will be repeated 4 times at 3 sites to achieve a final targeted baseline sample of 400 participants (i.e., 2 interventions x 3 sites x 4 replications x 17 participants = 408 participants). Outcome measures will be obtained at baseline, 2, 6, 12 and 18 months (see Figure 2, Projected Consort Flow Diagram, Appendix C).

**Settings**—We will partner with the Chicago Park District and Westside Health Authority (WHA) to conduct the trial. Although we require 3 sites to conduct the trial, the Park District has identified 4 sites that can participate, and WHA has identified 1 site. The Park sites include Smith Park (Northwest), Wicker Park (Northwest), Washington Park (Southeast), and Columbus Park (Southwest), and the WHA site includes their location on the westside (see more information about the sites in Appendix D). **All sites are staffed by nationally certified exercise instructors who will be trained separately to conduct either customary Fit and Strong! or Fit and Strong! Plus. (See letters from [name], CEO, Chicago Park District from [name], CEO, National Recreation and Park Association, and from [name], CEO, Westside Health Authority in Section 14).**

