**Randomization**—After obtaining informed consent, participants will be assigned to Fit and Strong! or Fit and Strong! Plus using a randomized block design with blocks consisting of approximately 17 participants at each of the 3 sites. Within each block we will stratify by American College of Rheumatology (ACR) functional classes (I, II, or III) to achieve balance on arthritis severity by group. The random permutation of block sizes will help to minimize manipulation of an assignment.

**Inclusion/Exclusion Criteria**—*Inclusion criteria* include LE OA (hips, knees, ankles, feet, lower back), age 60+, no current participation in a regular exercise program, a calculated BMI of  $>=25 - 50 \text{ kg/m}^2$  (upper limit used in ORBIT) ([name] et al., 2010) and willingness to participate in measurement and intervention procedures. The study rheumatologist will examine participants at the baseline interview to confirm presence of LE OA and determine ACR functional class. *Exclusion criteria* include severe cardiovascular disease, active thrombophlebitis, recent pulmonary embolus, an acute systemic illness, poorly controlled diabetes, other health conditions that might preclude exercise training, age  $<60$ , current participation in organized PA, uncomplicated hip or knee surgery within the previous 6 months or complicated surgery within the past year, steroid injections in either knee or hip within the previous three months, or diagnosis of rheumatoid arthritis. Participants with blood pressure readings 180/110 mm Hg or higher or 90/50 mm Hg or lower will be excluded.

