**Intervention Instructors**—*Exercise instructors delivering the programs will be certified by at least 1 of 10 possible nationally recognized certification bodies* (e.g., ACSM, ACE, etc.). Certified exercise instructors (CEIs) will be trained separately to conduct either Fit and Strong! or Fit and Strong! Plus. The CEIs will lead exercise sessions, maintain participant attendance records, and negotiate participant adherence plans during week 6. They will also facilitate the group problem solving sessions (see Fit and Strong! Plus Instructor Manual in Appendix F). If both programs are offered at the same site on the same day, we will schedule one program in the morning and the other in the afternoon to minimize contact between both participants and instructors. An alternative will be to schedule one program Mon, Weds, Fri and the other Tues, Thurs, Sat. Instructors for customary Fit and Strong! will participate in *an 8-hour training protocol* that we developed and refined over multiple studies. The protocol reviews theories used to design Fit and Strong!, findings from completed research, along with detailed information and hands-on modeling of the exercise components (warm ups, flexibility, aerobic conditioning, strength training, cool down), role playing group problem solving processes, and negotiating PA contracts. Fit and Strong! Plus instructors will participate in *a 12-hour training protocol* for Fit and Strong! Plus that includes the full Fit and Strong! instructor training plus training on *diet and weight management*. The training will cover the *contribution of excess weight to disability and exacerbation of OA symptoms, the significance of a minimum 5% weight loss* for this population, components of a healthy diet, the new USDA my plate (choosemyplate.gov), food shopping on a budget, healthy meal preparation, handling situations that trigger impulse eating, tips for healthy eating at restaurants, ethnic eating, cultural aspects of eating preferences, and choosing foods at special occasions. **Drs. [name] and [name], both of whom participated in the pilot training, developed the draft protocol.** The protocol includes role play for facilitating diet-focused group discussion/problem solving sessions and negotiating *PA and diet adherence contracts* (see Instructor Training, Appendix G).

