where  $Y_{it}$  represents a particular outcome variable for person  $i$  at time  $t$ , *Plus* is a dummy variable for the Fit and Strong! Plus effect, relative to customary Fit and Strong!, *Plus\*Time* represents the interaction with time, *ARA* is a covariate,  $u_i$  is the random effect for person  $i$  and  $e_{it}$  is a person-time specific error term. The *Plus\*Time* interaction tells us whether the rate of change with respect to time is greater (or less) in the Plus condition compared to customary Fit and Strong!. As shown, the model is for a continuous outcome, but it can be estimated for a wide variety of outcome variables (e.g., logistic regression and ordered logistic regression models). Time can be represented in multiple ways in addition to the simple linear effect shown here. By including the square of time we can test whether the effects of time are non-linear, and by including properly coded dummy variables for discrete time, we can test more specific hypotheses regarding non-linear effects. A crucial assumption of such models is that the person-specific error term,  $u_i$ , is uncorrelated with the remaining variables, which is plausible given the randomized design. The model, as written, assumes an “exchangeable” correlation matrix among the errors. However that assumption can be relaxed by using simple auto-regressive or Toeplitz (banded) correlation structures. All analyses will be done using Stata.

Analyses of secondary outcomes will examine the magnitude of between and within group differences at all time points to determine whether the addition of a diet component to Fit and Strong! benefits these outcomes (as expected) or is neutral or harmful with respect to certain outcomes. Exploratory analyses will evaluate movement on the new readiness for total joint replacement measure, and will examine patterns and trends in healthcare utilization, healthcare cost, and quality of life between and within the two study groups.

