**Table 6. Design Considerations**

Design Decisions	Rationale for Decision
1. Fit and Strong! plus is shorter than interventions in the literature.	Our goal is to incorporate common elements from longer interventions into one that is translatable. We include experts in weight loss intervention trials ([name]) and dietary assessment ([name]) in this effort. Fit and Strong! Plus has the same number of diet sessions (16) as the ADAPT diet/PA arm but in a format that is scalable.

2. We propose to recruit 400 older adults.	To meet this goal, we will use multiple strategies that succeeded in our prior work. We will set and closely monitor recruitment benchmarks and search for new community partners in this effort if needed.
3. We plan to follow participants for 24 months.	Our team has a 90% retention rate at 18 months. We will set retention targets and closely monitor success in meeting them. We will provide participant incentives and a lottery/cash voucher at each posttest, and we will conduct posttests at intervention sites in participants' neighborhoods.
4. Interventions are delivered by multiple instructors at multiple sites.	Our team has experience conducting training and conducting treatment fidelity checks for intervention trials. We have an established protocol to monitor fidelity and will extend this expertise to the new Fit and Strong! Plus intervention. A multi-instructor, multi-site approach will provide a more realistic assessment of feasibility for moving to scale.
5. Unanticipated consequences.	We have condensed the PA content of customary Fit and Strong! to reduce redundancy and allow space for new diet/weight loss content. We believe it unlikely that the changes will reduce the impact on PA maintenance and outcomes previously seen in Fit and Strong! trials. However, we will monitor this issue closely through fidelity checks and also use two-tailed tests to examine unexpected consequences of these changes.

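### The plan does not say how instructors are assigned to the two programs, and its model has no instructor term, so skill-related selection would bias the arm comparison

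*Combined protocol and SAP*

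**What the plan says.** - **Instructors.** Intervention Instructors states: "Certified exercise instructors (CEIs) will be trained separately to conduct either Fit and Strong! or Fit and Strong! Plus". Settings repeats it: "All sites are staffed by nationally certified exercise instructors who will be trained separately". Training lasts 8 hours for the customary program and 12 for Plus; the longer course contains the shorter one and adds diet and weight management. Classes are timed to keep the two sets of instructors apart. Instructors lead the exercise, run the group problem solving and negotiate each participant's maintenance plan in week 6.
- **How many.** No number is given. Table 6 says only: "Interventions are delivered by multiple instructors at multiple sites". The layout is "2 interventions x 3 sites x 4 replications x 17 participants = 408 participants", which makes 2 x 3 x 4 = 24 classes, 12 per arm.
- **What is randomised.** Randomization describes allocation within site: "participants will be assigned to Fit and Strong! or Fit and Strong! Plus using a randomized block design with blocks consisting of approximately 17 participants". The available text describes nothing comparable for instructors.
- **Analysis.** In the Data Analysis model the only random term besides the residual "is the random effect for person". There is no term for instructor, class or site, and the Power Analysis makes no allowance for clustering.
- **Safeguards.** Table 6: "We have an established protocol to monitor fidelity and will extend this expertise to the new Fit and Strong! Plus intervention". Table 5 lists checklist site visits in Week 4 and tracks instructor attrition.

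**The concern.** Instructors are nested in arm, so the arm contrast compares two programs and two groups of teachers at once. Randomising participants balances the participants, not the teachers.

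The two courses differ in length and content. If sites or trainers decide who takes which, interest in weight management or experience could plausibly play a part. Stronger instructors in Plus would overstate weight loss. Stronger instructors in the customary arm would hide a diet effect, and could make the condensed activity content look harmful, which is the unintended consequence that Table 6 says the team will watch for.

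Two mechanisms need to be kept apart. A systematic difference from selection shifts the estimate, and no variance term repairs it. A chance difference among instructors is extra variance, which a suitable model can carry into the standard error. The plan as written addresses neither.

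**Working it through.** **1. The plan's own figure.** The Power Analysis needs about 300 participants for an effect of .2, power .9, two-tailed, cross-time correlation .9 and 5% attrition per time point. Alpha is not stated; .05 is assumed here. For a baseline-to-end change, the SD is sqrt(2 x (1 - .9)) = .447, and n per arm = 2 x (1.96 + 1.282)^2 x .2 / .2^2 = 105.1. With the t correction this is 106, or 212 in total, and 212 / .95^4 = 260. A linear-trend contrast gives 185 to 198 under an exchangeable structure and about 750 to 890 under AR(1). The 300 is not reproduced, but it is not shown to be wrong either, because alpha and the full covariance structure are not given. None of these versions includes instructors, and the point does not depend on the figure.

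**2. Inputs.**
- From the documents: effect .2, correlation .9, 3 sites, 400 participants (200 per arm).
- Assumed: one instructor per program per site (3 per arm), instructor ICC for weight change of .02 to .05, and a probability q that the better of a site's two instructors goes to the same arm.

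**3. Bias.** The better and worse of two normal draws differ on average by 2/sqrt(pi) = 1.128 SDs. So bias = (2q - 1) x 1.128 x sqrt(ICC) x .447.

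| q | ICC .02 | ICC .05 | share of .2 |
|---|---|---|---|
| .5 (random draw) | 0 | 0 | 0 |
| .6 | .014 | .023 | 7% to 11% |
| .75 | .036 | .056 | 18% to 28% |
| 1 (upper bound) | .071 | .113 | 36% to 56% |

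**4. Type I error of the person-only model, 400 participants, final-visit change.** Its standard error is .447 x 2/20 = .0447, so it rejects when the difference exceeds 1.96 x .0447 = .0877 in size.

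*Random draw alone.* True variance = 2 x ICC x .2/3 + 2 x (1 - ICC) x .2/200.
- ICC .02: .00267 + .00196 = .00463, SD .0680; .0877/.0680 = 1.29, type I error 20%.
- ICC .05: .00667 + .00190 = .00857, SD .0926; .0877/.0926 = .947, type I error 34%.

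*Better instructor to one arm 3 times in 4.* The expected squared gap per site is 2 x ICC x .2. Subtract the squared bias, divide by 3 and add the within part.
- ICC .02: (.008 - .00127)/3 + .00196 = .00420, SD .0648, mean .036; type I error 24%.
- ICC .05: (.020 - .00318)/3 + .00190 = .00751, SD .0866, mean .056; about 41% by normal approximation, 42% by simulation.

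With the plan's attrition (200 x .95^4 = 163 per arm), the draw-alone figures become 17% and 31%.

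**5. Adding the instructor term.** After a random draw, an instructor-level analysis has a type I error of about 5%. Power for .2 with 163 per arm and 2(k - 1) degrees of freedom, where k is the number of instructors per arm:

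| k | ICC .02 | ICC .05 |
|---|---|---|
| 3 | .57 | .37 |
| 6 | .84 | .67 |
| 12 | .93 | .86 |

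Ignoring instructors, the nominal power is .98. Without a draw, the term leaves the bias in step 3 where it is.

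**The case against.** A reader might infer that assignment is left to choice. The documents do not say so; they are silent. Parts of the Approach section were not available for this check, including the text just before the sample-size arithmetic, and a rule could stand there.

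A reader might also infer that there are only a few instructors. With 12 classes per arm there could be up to 12 in each, and tracking instructor attrition suggests that turnover is expected. Three per arm is an assumption. More instructors shrink chance imbalance, but not systematic selection.

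Nor does every difference in skill become a bias beyond analysis. With several instructors per arm, chance differences are variance that a random effect can carry.

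It is tempting to present the draw as a complete cure. Treating the bias as a constant gives a type I error of 13% to 24%, which invites comparison with 5%. That omits instructor variance: under the same assumptions the draw alone moves the rate only from 24%-42% to 20%-34%. The mean absolute instructor imbalance falls only from .049-.077 to .041-.065 SD.

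The safeguards are real: both programs at each site, identical exercise routines, national certification, a Plus course containing the whole customary course, and fidelity checks. They limit differences in delivery. They do not balance skill between arms, and the Week 4 visit comes before the week 6 negotiation.

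The ICC and the steering probabilities have no source in the documents, and at 6 in 10 the bias is only 7% to 11% of the planned effect. That limits the size of the concern but does not remove it.

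**Conclusion.** The concern holds as a gap in design and analysis. Each instructor is tied to one program, no assignment rule appears in the available text, and the model has no instructor or class term. Selection related to skill would be confounded with arm and could not be removed afterwards.

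The size is illustrative. It rests on one instructor per program per site, an ICC of .02 to .05, 3-in-4 steering and a two-sided .05 test. The missing variance term accounts for most of the type I error inflation, and the draw is what removes the expected bias, so the two remedies belong together. The documents do not support saying that the comparison is biased, only that nothing described prevents it.

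**What to change.** 1. In Intervention Instructors, state that where a site has eligible instructors willing to teach either program, the one trained for Plus is drawn at random within that site, with a new draw when instructors join.
2. Report the number and experience of instructors by arm.
3. Add an instructor (or class) random effect, with small-sample degrees of freedom, to the Data Analysis model.

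If instructors have already been assigned, report how this was done and add the term.

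**Cost.** One draw per site and a few sentences. An instructor unwilling to teach either program may be passed over, which matters more where site staff are few. Standard errors widen by an amount that depends on the number of instructors. At 200 per arm, the standard error rises from .0447 to sqrt(2 x (.02 x .2/12 + .98 x .2/200)) = .0513 with 12 per arm and an ICC of .02, and to .0926 with 3 per arm and an ICC of .05. If there are only about three per arm, the loss of power is substantial and should be known before the analysis. The term does not create that uncertainty; the person-only model leaves it out.

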**Education/Behavior Change—This is where the two programs diverge:**

**Fit and Strong!** The health education component of Fit and Strong! bolsters SE for exercise and SE for exercise adherence over time and in the presence of barriers. It also addresses SE to manage pain and other arthritis-related symptoms. The curriculum consists of 24 sessions that address OA, the use of PA to manage OA symptoms, basic elements of a balanced exercise program, exercising safely with OA, barriers to PA maintenance, and strategies to overcome common barriers.

In customary Fit and Strong!, participants meet with instructors in week 6 to review individual preferences for a follow-up PA maintenance plan. The plan meets minimal criteria for 90 minutes each of flexibility, aerobic and resistance training per week after Fit and Strong! ends. In negotiating the contract, instructors follow the Jensen and Lorish (1994) process model for patient-practitioner collaboration. Instead of prescribing a post-training regimen, instructors ask “what is the best regimen that this participant is likely to follow?”, and follow up with negotiation and iterative problem-solving, including discussion of the participant’s belief that the exercise will accomplish a valued goal. The emphasis is on building skills and identifying strategies that will assist participants to maintain adherence. Participants are encouraged to supplement exercises learned in Fit and Strong! with other PA like swimming, gardening, mall walking, etc.

**Fit and Strong! Plus.** In addition to the activities described above for the health education component of the customary program, Fit and Strong! Plus also addresses SE for diet behaviors and **includes techniques to achieve a minimum 5% weight loss (see Instructor Manual, Appendix F). The goal is to increase consumption of fruits and vegetables, decrease percent energy from saturated fats, decrease consumption of sugar sweetened drinks, and reduce overall caloric consumption such that participants will achieve a minimum 5% weight loss at 6 months that will be maintained over time—the same dietary goals achieved by the ORBIT trial.** To boost SE for diet, we ask participants at baseline to specify dietary and weight outcomes that they plan to achieve through participation in Fit and Strong! Plus. Week 1 addresses the relationship between OA, obesity, and disability, and stresses the importance of a 5% decrease in weight. The instructor lets participants know that the remainder of the program will provide the tools that will help them achieve this goal. **During Week 1, all participants receive The Calorie King Calorie, Fat, and Carbohydrate Counter ([www.CalorieKing.com](http://www.CalorieKing.com)) that lists calories and fat contained in popular foods. Participants are taught how to use the book to fill out food diaries in which they record all food consumed during Week Two. Participants bring the food diaries to class where their content is discussed during classes 5, 6 and 7. The diary documents all food eaten daily, including portion size, time of day, where and with whom food was eaten, other activities while eating, and mood. Participants calculate the number of pounds that they need to lose over the next 6 months to achieve a minimum 5% weight loss. Participants who weigh <= 250 lbs. are asked to adhere to 1200-1500 calories per day and persons who weigh more than 250 lbs. are asked to adhere to 1500-1800 calories per day. All participants are urged to consume foods that contain no more than 3 grams of fat per serving. Participants are encouraged to maintain the diary on their own after Week 2 and are given diaries to maintain at graduation from the class in session 24. Weight is measured weekly on a scale that remains at the study site.** Food diaries and routine weigh-ins help participants track progress over time, increasing awareness of dietary habits and motivating participants to modify habits to meet goals.

The customary Fit and Strong! health education curriculum devotes 24 sessions to topics related to PA and arthritis. The Fit and Strong! Plus Manual condenses the PA/arthritis sessions from 14 to 7 and adds 7 new sessions addressing specific dietary topics. These include: Healthy Eating, Reading Labels, Grocery Shopping, Healthy Cooking, Healthy Meals, Handling Triggers, and Getting Past Barriers to Healthy Eating. **Where possible, each diet session also includes a homework assignment that enables participants to try a technique at home and bring results back to class to share and refine.** Of the remaining 17 sessions, 9 address combined PA and diet content, 7 focus on PA alone, and 1 is devoted to the negotiated adherence contract. Thus, Fit and Strong Plus! puts equal emphasis on diet and PA. **Notably, the 16 dietary/weight loss sessions in Fit and Strong! are identical to the dose used in the ADAPT trial. Table 1 in Appendix H compares content for Fit and Strong! and Fit and Strong! Plus to the ADAPT/ ORBIT trials. Table 2 in the same Appendix compares program dose.** The PA maintenance contract has been expanded to include actions planned to maintain diet changes and weight loss. Session 17 “Healthy Meal Ideas” requires participants to bring a healthy recipe to share with the class and the last session asks participants to bring

healthy dishes to share. The recipes shared during session 17 are printed, bound, and returned to participants following a graduation ceremony on the last day of class. Participants also receive their manuals, ankle weights, exercise bands, and food diaries.

***Participants in Fit and Strong! Plus meet with the instructor during week 6 to develop a negotiated PA plus weight management maintenance contract. The instructor uses the same process model as in Fit and Strong! to arrive at a realistic diet/weight loss maintenance plan. The review includes strategies to 1) include more fruits and vegetables daily, 2) decrease consumption of fat, 3) decrease sugar sweetened beverages, and 4) decrease overall caloric consumption by dealing with triggers, selecting healthy snacks, making shopping plans, etc. The review can include referral to community programs like Weight Watchers if participants express a preference for ongoing structured group-based reinforcement. In cases of both Fit and Strong! and Fit and Strong! Plus our goal is to enroll participants who are at high risk of mobility disability, help them adopt healthy behaviors over 8 weeks, and then help them to develop personalized maintenance strategies that have substantial probability of long-term adherence.***

**Maintenance boosters**—Maintenance of behavior will be reinforced in both groups during months 3 through 24 using tapered TR. Using methods tested in our effectiveness trial ([name] et al., 2010), we will recruit 2 Master's of Public Health student research assistants (RAs) well versed in health education techniques. One student will work with customary Fit and Strong! participants, and the other will work with Fit and Strong! Plus participants using scripted protocols. RAs will be trained separately. A two-week training program will include 1) reading materials related to successful PA or PA and weight loss maintenance interventions; 2) an overview of intervention objectives; 3) a review of each week's curriculum; and 4) role playing dealing with frustrations and barriers inherent in achieving physical activity or physical activity / weight loss maintenance. The Project Manager will meet with RAs bi-weekly to debrief calls, provide feedback and guidance, and revise the protocols as needed. To monitor call quality, she and the study PIs will listen to a sample of calls made by each RA periodically. All participants will receive one call during months 4, 8, and 15. Newsletters will be mailed each quarter to study participants. The newsletter will reinforce materials learned in class about physical activity and diet related topics.

***TR for Customary Fit and Strong!*** The RA will review participants' original or amended contract, participation in exercise since the last call, barriers experienced, motivation for exercise, exercise efficacy, and recent symptoms (pain, stiffness). Adverse events will be documented and reported to the PIs. The RA will tailor call content to problems identified by participants and will support participants' long-term maintenance of regular exercise. If participants are in maintenance, calls will focus on helping them to stay motivated and will support SE for exercise. If participants are experiencing difficulties, calls will address barriers and ways to reactivate participation. The RA will review benefits of PA and provide information regarding local exercise programs. Based on prior work, we expect each call to take 15 minutes.

***TR for Fit and Strong! Plus.*** In addition to the activities described above, the diet/PA calls to Fit and Strong! Plus participants will also address weight management and weight loss goals, success, challenges, and barriers. The RA will ask for self-reported weight and discuss progress toward weight loss goals. If participants are in maintenance, calls will reinforce this success in the same manner described above. If participants report difficulty, calls will explore the circumstances of relapse and engage participants in strategizing ways to get back on track, and provide information about local programs. These calls will be longer than calls for customary Fit and Strong! participants because they will address both PA and weight loss goals. Drs. [name] and [name] will collaborate on developing the training protocol for the Fit and Strong! Plus RA, participate in training, and review a subset of calls.

We realize that the translation of TR to real world settings is problematic, but believe it is important to use this methodology in the trial. If Fit and Strong! Plus is successful, we believe it will be possible to refer participants to existing web-based diet and PA messages (i.e., everydayhealth.com) rather than TR. We will explore participant Internet access during the trial and will also explore the production of a booster DVD in study out years.

